Study protocol

Effect of Influence of invasiveness of subgingival debridements on attachment gain after anti-infective periodontal therapy (ATTGAIN16)

V1.2 vom 16.3.2016

Introduction

The main issue of non-surgical as well as surgical periodontal therapy is the elimination of vital and mineralized bacterial biofilm by mechanical plaque removal. Particularly in the context of surgical periodontal therapy, the mechanical plaque removal is accompanied by the disposal of granulation tissue.

Current studies, however, suggest that this may be a wrong approach, since the deeper, infra-alveolar soft tissue of periodontal lesions ≥ 5 mm probing depth seems to have a pronounced regenerative capacity after resolution of the periodontal inflammation⁴⁻⁶.

The conventional manual instrumentation of the root surfaces with curettes or ultrasound scaler resolves the root cement in a layer thickness of on average 24 ± 18 μm , respectively 20 ± 15 μm ⁹. However, the opportunity of a regenerative Reattachment would be improved significantly by the retention the root cement.

Therefore, the aim of any minimal invasive periodontal therapy is the elimination of the soft/vital bacterial biofilm with the least possible preservation of the existing cement layer with the disclaim of surgical approaches and the explicit elimination of granulation tissue.

In this context the use of subgingival air polishing devices seems to be a promising option^{10 11}. Various studies have confirmed the efficiency of subgingival air polishing devices for biofilm removal in a comparable magnitude to ultrasound scales or a combination of hand instruments and ultrasound scales¹¹⁻¹³. By using a subgingival air polishing devices Bacterial plaque can be removed up to a pocket depth of 5 mm

without damaging the treated root surfaces^{14, 15}. Also an alternative cleaning powder of smaller grain size based on the sugar alcohols Erythritols has been performed successfully in randomized clinical trials^{16, 17}.

Study objective

This study aims to evaluate whether a two-stage anti-infective periodontal treatment strategy, comprising a minimally invasive removal of only soft microbial biofilms with an air polish in the first step and a debridement of subgingival dental calculus with air-scaler and abrasors in a second step, results in a greater reduction of the periodontal attachment level, than a single step strategy, with a sub and supragingival mechanical debridement of soft and mineralized bacterial biofilms at the same time.

The study will be conducted with periodontal patients with deep infra-bony defects.

Material und Methoden

study population

Patients of both sexes with untreated, severe chronic or aggressive periodontitis will be recruited for the study.

inclusion criteria

- at least 15 natural teeth still in situ
- at least 1 tooth with periodontal pocket depths ≥ 6 mm and infra-alveolar bone defect
- Age ≥ 18 years

exclusion criteria

- systematic periodontal therapy ≤ 12 months before the screening time

- need for antibiotic prophylaxis before dental care
- untreated systemic diseases that interfere with periodontal healing (eg: uncontrolled diabetes mellitus).

Study design

1. Baseline examination and group assignment

All patients who meet the inclusion criteria, will be informed about the study objectives and will give their written consent.

The following parameters will be recorded at the beginning of the study on all teeth:

1. Probing Attachment Level (PAL)

(6 sites: mesiobuccal, buccal, distobuccal, mesiooral, oral, distooral)

2. Probing Pocket Depth (PPD)

(6 sites: mesiobuccal, buccal, distobuccal, mesiooral, oral, distooral)

3. Bleeding on probing (BoP) (6 measuring points / tooth)

(6 sites: mesiobuccal, buccal, distobuccal, mesiooral, oral, distooral)

4. Gingival Index (GI)

(each 1 measuring point on the buccal tooth surfaces)

5. Plaque Control Record (PCR)

(4 measuring points: mesial, buccal, distal, oral)

Subsequently, microbial samples will be taken from the deepest gingival pocket per jaw quadrant with the help of sterile paper tips and stored in Eppendorf tubes at -20 C until further analysis.

After baseline examination, the study patients will be randomly assigned to the test or the control group with a computer-generated block randomization list. Randomization will be stratified for smokers and non-smokers.

Antiinfective therapy

The anti-infective therapy will be scheduled promptly within a maximum of 10 days after the Baseline Visit.

Antiinfective therapy test group:

All patients of the test group receive a supra- and subgingival removal of all tooth adherent soft bacterial biofilms in 1-2 sessions, but within 24 h, with a low-abrasive erythritol-based cleaning powder (Air-Flow Pulver Plus, EMS, Nyon, Switzerland). Only supra- and paragingival calculus will be dislodged with sonic / ultrasonic scalers. The presence of subgingival calculus will only be documented. However, an additional mechanical subgingival instrumentation of exposed root surfaces by scaling and root planing to remove subgingival calculus will not be performed at this time.

Antiinfective therapy control group:

All patients of the control group receive a supra- and subgingival removal of all tooth adherent soft bacterial biofilms in 1-2 sessions within 24 h too, but by using hand scalers and curettes, sonic / ultrasonic scalers, rubber cup and polishing paste. In contrast to the test group, all exposed subgingival root surfaces will be instrumented to remove all adherent mineralized subgingival calculus.

1. Reevaluation

The 1st re-evaluation is scheduled 28 days (+ 7 days) after completion of anti-infectious periodontal therapy.

PAL, PPD, BoP, GI, and PCR will be re-recorded on all teeth and for patients from the test and the control group and subgingival microbial samples of the deepest pockets in each quadrant will be taken again. Plaque will subsequently be visualized by staining. All patient gains oral hygiene instructions to improve the efficiency of domestic plaque control by appropriate brushing techniques and aids (dental floss / interdental brushes).

All patients of in the test group, will receive a subgingival instrumentation using curettes or ultrasound scalers to subduct the subgingival calculus which just has been documented initially, but not removed.

2. Reevaluation

The 2nd reevaluation is scheduled 56 days (+7 days) after the 1st reevaluation visit.

The parameters PAL, PPD, BoP, GI and PCR will be reassessed in all study patients again. Any remaining oral hygiene deficiencies will be rediscovered by staining, and oral hygiene instructions and suitable brushing techniques will be demonstrated again. Teeth persistent bleeding on probing during reevaluation visit will be subgingivally instrumented with curettes or ultrasound scalers in the control group. The test group will receive a subgingival air polish cleaning with the low-abrasive erythritol-based cleaning powder.

Close out visit

168 days \pm 7 days after the first visit (84 days after the second reevaluation), the close out visit is scheduled. The parameters PAL, PPD, BoP, GI and PCR will be reassessed again and microbial samples from the deepest gingival pocket per quadrant will be taken again.

Microbiological analyzes

The collected pooled microbiological samples will be analyzed for the presence of the periodontitis-associated microorganisms *Porphyromonas gingivalis*, *Tannerella forsythia*, *Treponema denticola* and *Aggregatibacter actinomycetemcomitans* using a commercially available bacterial gene probe test (Carpegen Perio Diagnostik, Carpegen GmbH, Münster). It is also planned to carry out a total genome sequencing of the subgingival microbiome taken from the pockets on all collected microbial samples.

Statistical analysis

Primary endpoint

The primary endpoint of the study is the reduction of the probing attachment level (PAL) between baseline and the final study after 168 days.

Secondary endpoints

As secondary endpoints the pocket depth (PPD), bleeding on probing (BoP), the gingival index (GI), the plaque control record (PCR), and changes in the composition of the subgingival pocket microflora will be evaluated.

Sample size

Assuming an average reduction of an attachment level of -2.0 mm in the control group between baseline and second reevaluation and an assumed standard deviation of ± 0.6 mm, the difference between the test and control group is 0.6 mm for a test strength of 0.9 and an error probability of $p \leq 0.05$, a group size of 2×22 patients is required.

References

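### Do the 168-day and 84-day timings of the close-out visit conflict in a way that harms the primary endpoint?

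*Combined protocol and SAP*

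**What the plan says.** Close out visit gives 168 days, with a margin either side, as "7 days after the first visit (84 days after the second reevaluation), the close out visit is scheduled". The margin is ± 7 days and is attached to the 168; the 84 in parentheses has none.

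Primary endpoint defines the outcome as "the reduction of the probing attachment level (PAL) between baseline and the final study after 168 days", so the close-out visit supplies the primary measurement.

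The earlier steps are timed as follows:

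- Antiinfective therapy: treatment is "scheduled promptly within a maximum of 10 days after the Baseline Visit".
- Antiinfective therapy test group: treatment is given "in 1-2 sessions, but within 24 h"; the control group has the same limit.
- 1. Reevaluation: "The 1st re-evaluation is scheduled 28 days (+ 7 days) after completion of anti-infectious periodontal therapy".
- 2. Reevaluation: "The 2nd reevaluation is scheduled 56 days (+7 days) after the 1st reevaluation visit".

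The documents do not define *first visit*, and they do not say which close-out figure prevails if the two differ.

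**The concern.** One sentence gives two starting points for the visit that matters most. The figures agree exactly only when nothing is late, and the sum 28 + 56 + 84 counts from completed therapy, whereas the endpoint sentence can be read as counting from baseline. Up to 10 days may lie between those two points. Both re-evaluation windows run late only, so an early visit cannot win back a delay.

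A patient who keeps every earlier window could therefore reach a close-out date that satisfies one figure and breaks the other. At stake would be an unclear time point for the primary measurement, unclear deviation status, and a variable interval between the second re-evaluation, where further subgingival treatment is given, and the final attachment measurement.

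**Working it through.** **Inputs.** Baseline to completed therapy: 0 to 10 days, or 11 if a second session falls on the next day (Antiinfective therapy). Therapy to first re-evaluation: 28 to 35 days. First to second re-evaluation: 56 to 63 days. Close-out: day 161 to 175 (168 ± 7) from the first visit; also 84 days after the second re-evaluation.

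**1. The plan's own figure.** 28 + 56 + 84 = 168. It reproduces, with every delay at zero.

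**2. Delays.** Let D be the total permitted delay from the chosen starting point. The second re-evaluation falls on day 84 + D, and 84 days later is day 168 + D.

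- From baseline: D is at most 10 + 7 + 7 = 24 (25 with a next-day session).
- From completed therapy: D is at most 7 + 7 = 14.

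**3. If the 84 days is binding and exact.** Conflict arises when 168 + D > 175, that is, D > 7.

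- From baseline the worst case is day 168 + 24 = 192, which is 192 − 175 = 17 days past the window (18 with a next-day session).
- From completed therapy it is day 168 + 14 = 182, which is 7 days past.
- Therapy completed on day 8, 9 or 10 with both re-evaluations on target gives day 176, 177 or 178 from baseline. Counted from completed therapy, the same patients arrive exactly on day 168.

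**4. If the ± 7 also covers the 84 days.** The earliest allowed date is 168 + D − 7 = 161 + D. Conflict needs 161 + D > 175, that is, D > 14. This can be reached from baseline but not from completed therapy.

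**5. If the 84 days is nominal.** The second re-evaluation falls by day 84 + 24 = 108 (109), before day 161, so every patient can meet the window. At maximum delay the interval to close-out is 161 − 108 = 53 to 175 − 108 = 67 days (52 to 66 with a next-day session). From completed therapy the latest second re-evaluation is day 98, which leaves 161 − 98 = 63 to 175 − 98 = 77 days.

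**6. Share of permitted whole-day schedules in conflict.** From baseline there are 11 × 8 × 8 = 704 combinations of delay, and 120 of them total 7 days or less. From completed therapy there are 8 × 8 = 64, of which 36 total 7 or less.

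| Starting point | 84 exact | 84 ± 7 | 84 nominal |
|---|---|---|---|
| Baseline | (704 − 120)/704 = 584/704 = 83% | 212/704 = 30% | 0 |
| Completed therapy | (64 − 36)/64 = 28/64 = 44% | 0/64 | 0 |

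These shares weight every permitted schedule equally and do not forecast patients; the documents give no distribution of visit dates. If, from baseline, each re-evaluation is at most 3 days late, the shares are 96/176 = 55% with 84 exact and 4/176 = 2.3% with 84 ± 7.

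**The case for a change.** The strongest case for a change is that the text never calls the 84 days nominal, and that a protocol should not leave a site to choose between two dates for its primary measurement. If the 168-day figure governs, the interval since the second re-evaluation can shrink from 84 days to as little as 53 (52 with a next-day session). Both arms can receive further subgingival treatment at that visit, so the healing time before the final measurement would differ from the plan's own figure. Correcting it would cost only a few words.

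Part of this stands. *First visit* is undefined, precedence is unstated, and the interval before close-out will vary between patients. If the sponsor means the 84 days to bind, the passages contradict each other at longer delays and must be reconciled; which figure governs is for the sponsor to say.

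The step from there to a flaw in the analysis does not stand. The tolerance sits on one figure only, and the other is exactly what is left after 28 and 56 days, which is how a planned remainder is usually written. Nor does it take therapy on the day of baseline for the baseline reading to work: with on-target re-evaluations, therapy completed on any day from 0 to 7 satisfies both figures, because the ± 7 absorbs the gap. The endpoint sentence may also simply name the two measurements and label the final visit, without counting days from baseline.

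**Conclusion.** No change follows. The arithmetic of a possible conflict is right, but it depends on treating a parenthesis without a tolerance as a second binding requirement. Read as the planned remainder, the sentence leaves every patient able to comply.

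On any reading, no harm to the comparison is shown. The windows are identical in both arms, so the permitted spread in timing does not favour either. No rule excludes an out-of-window visit, so an ambiguous deviation status would not remove a patient from the primary analysis. The sample size rests on a difference of 0.6 mm and a standard deviation of 0.6 mm and takes no input from the close-out date. No effect on the attachment measurement is demonstrated.

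The size of the issue is an overshoot of at most 17 to 18 days if the 84 days binds exactly and counting starts at baseline, at most 7 days counting from completed therapy, and none if it is nominal. This conclusion assumes that visits are booked without regard to arm and that staff apply one reading throughout. Defining the starting point and labelling the 84 days would tidy the text, but it would only write down what a trial team would settle in practice.

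### Does the primary endpoint need a named set of PAL sites, and planning values restated for day 168, before 2×22 can stand?

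*Combined protocol and SAP*

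**What the plan says.** The Primary endpoint paragraph under Statistical analysis reads: "The primary endpoint of the study is the reduction of the probing attachment level (PAL) between baseline and the final study after 168 days". It names a variable and a time span, but no sites, teeth or summary.

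The baseline section lists PAL at six sites per tooth on all teeth. The section on the first reevaluation repeats the full record: "PAL, PPD, BoP, GI, and PCR will be re-recorded on all teeth". Entry requires a minimum of 15 teeth, and at least one tooth with a pocket of 6 mm or more and a bone defect. The Study objective adds: "The study will be conducted with periodontal patients with deep infra-bony defects".

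The Sample size paragraph begins "Assuming an average reduction of an attachment level of -2.0 mm in the control group between baseline and second reevaluation", takes an SD of 0.6 mm and a difference of 0.6 mm, and concludes that "a group size of 2×22 patients is required".

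The section on the second reevaluation then gives a further treatment that differs by arm. For control: "Teeth persistent bleeding on probing during reevaluation visit will be subgingivally instrumented with curettes or ultrasound scalers in the control group". For test: "The test group will receive a subgingival air polish cleaning with the low-abrasive erythritol-based cleaning powder". The endpoint visit follows: "84 days after the second reevaluation), the close out visit is scheduled".

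**The concern.** Two things look wrong.

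The first is the endpoint variable. At least 90 PAL values per patient per visit must become one number, and the text does not say how. The Introduction expects regeneration in lesions of 5 mm or more, and the Study objective speaks of patients with deep defects. A mean over deep or infra-bony sites would therefore fit the rationale as well as a whole-mouth mean would fit the measurement schedule. These answer different questions. If the choice were left until the data were seen, the primary result could depend on it.

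The second is the planning visit. The only visit named in the Sample size paragraph is the second reevaluation, while the endpoint is at day 168. An arm-specific treatment step lies between them. If the 0.6 mm difference or the 0.6 mm SD also belonged to the earlier visit, or to another site set, the stated power of 0.90 would describe a quantity other than the one tested.

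**Working it through.** **Reproducing the plan's figure.** Inputs from the Sample size paragraph: difference 0.6 mm, SD 0.6 mm, power 0.90, alpha 0.05. The paragraph does not state sidedness; two-sided is the version that reproduces its number. With one value per patient:

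n per arm = 2 × (1.960 + 1.282)² × (SD / difference)² = 2 × 10.507 × (0.6 / 0.6)² = 21.01, rounded up to 22.

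At 22 per arm, power is 0.913 by the normal formula and 0.8997 by the noncentral t. A strict t-test calculation gives 23. One-sided testing would give 18, which does not match. The plan's number is therefore correct for a difference/SD ratio of 1.0 at patient level.

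**What the -2.0 mm does.** It does not appear in the formula. It is the only value explicitly tied to the second reevaluation. The difference and the SD stand in the same sentence with no visit of their own. Assigning them to the second reevaluation is a natural inference, but the text does not say so.

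**The visit gap.** The second reevaluation is nominally 28 + 56 = 84 days after therapy, and close-out is 84 days later. If every window is used, the second reevaluation falls on day 10 + 1 + 35 + 63 = 109 from baseline. Close-out at 168 ± 7 days from the first visit (161 to 175) is then 52 to 66 days later. The gap is thus nominally 84 days, and shorter when the windows are used.

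**Which sites.** Side by side:

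- For all recorded sites: six sites on all teeth are measured at every visit, the anti-infective treatment covers the whole mouth, the objective compares attachment level with no site restriction, and the sample size is in patients.
- For deep or infra-bony sites: the Introduction's rationale and the population line. The population line describes patients, not the sites analysed.

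The text taken as a whole favours the all-site mean.

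**Could -2.0 mm be an all-site mean?** One qualifying tooth is 6 of 90 sites (6.7%), but that is an entry minimum, and the study population is patients with untreated severe disease. The check needs a share f of deep sites, their mean gain g and the gain h elsewhere, with f × g + (1 − f) × h = 2.0. The documents give none of the three. Assuming h between 0 and 1.0 mm, g must be 3.0 to 4.0 mm if f = 0.5, and 6.0 to 10.0 mm if f = 0.2. The answer depends wholly on the assumed f, so it does not show the planning value to be implausible.

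**Sensitivity (assumed ratios).** Two-sided t test, alpha 0.05:

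| Difference/SD at day 168 | Power at 22 per arm | n per arm for 90% |
|---|---|---|
| 1.2 | 0.973 | 16 |
| 1.0 | 0.900 | 23 |
| 0.8 | 0.736 | 34 |
| 0.6 | 0.494 | 60 |

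This table holds for any two-arm comparison with 22 per arm. It shows what would follow from a different ratio, and is not evidence that the ratio differs here.

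**The case for a change.** The strongest case for a change is that a reader cannot rebuild the primary test from the text alone. The statistical section holds only endpoints and sample size, so nothing else supplies the site set. More than two site sets could be defended: all sites, sites above a depth cut, defect sites, or the deepest site. Wording would cost little, since every value is already recorded. The visit mismatch is in the document itself and needs no outside source.

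Much of this stands as description. The endpoint sentence is incomplete, and the visit named beside the control mean is not the endpoint visit. Advance wording would also close off a later choice of site set.

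It does not show that the planned analysis goes wrong. Patient counts fix the unit of analysis, and the schedule and objective supply the natural summary. An analyst who averages all recorded sites per patient and compares the arms has a valid test with the sample size as calculated. Asking the sponsor to choose a site set would not improve on that reading. The arm-specific step at the second reevaluation belongs to the strategies being compared, so an endpoint that includes it is no fault. The visit named beside the -2.0 mm may be a slip or a figure carried over from earlier follow-up. Either way, the group size does not depend on that number.

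**Conclusion.** No change to the plan follows. The missing site set is a gap that analysts fill sensibly with one all-site mean per patient. The visit named in the Sample size paragraph is attached to a value that does not drive the calculation. The 2×22 reproduces (21.01 rounded up; t-test power 0.8997), and the documents show no power loss.

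This rests on two assumptions: that the all-site mean is the quantity analysed, and that the 0.6 mm difference and 0.6 mm SD are meant for it at day 168. The documents neither confirm nor contradict the second. If the true ratio were 0.8, power would be 0.74; if it were 1.2, 0.97. Nothing in the text favours one over the other. A primary result reported on a selected set of sites would be a departure from the natural reading and should be judged as such.

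### No primary analysis is named; an ANCOVA of PAL change with baseline PAL and smoking stratum should be prespecified, as a cheap gain in precision rather than a cure for bias

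*Combined protocol and SAP*

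**What the plan says.** The statistical section of the combined protocol and SAP consists of the primary endpoint, the secondary endpoints and a sample size sentence. The primary endpoint is given as "The primary endpoint of the study is the reduction of the probing attachment level (PAL) between baseline and the final study after 168 days". No test, model, covariate or level of analysis follows, there or elsewhere.

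The sample size sentence begins "Assuming an average reduction of an attachment level of -2.0 mm in the control group between baseline and second reevaluation", takes an SD of 0.6 mm, and continues "the difference between the test and control group is 0.6 mm for a test strength of 0.9", with an error probability of 0.05. It arrives at 22 patients per group. It does not state whether the test is one- or two-sided, or whether the SD is that of a patient's change.

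Under Study design, in the item on baseline examination and group assignment, patients are allocated "with a computer-generated block randomization list", and "Randomization will be stratified for smokers and non-smokers". The same item introduces the clinical measurements with "The following parameters will be recorded at the beginning of the study on all teeth"; PAL heads that list, at six sites per tooth. Smoking status is not on the list, but it must be known for every patient if the stratification is to work. The inclusion criteria require "at least 15 natural teeth still in situ". No section says which sites enter the endpoint or how they are combined into one value per patient.

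**The concern.** Two variables that the design already secures, the smoking stratum and baseline PAL, are left out of the analysis because no analysis is described.

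If smoking affects attachment gain, stratified blocks make the arms more alike than simple randomisation would. A test that ignores the stratum still counts smoking variation as noise, so its standard error is too large and it rejects too rarely under the null hypothesis. If baseline PAL predicts change, leaving it out widens the confidence interval.

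There is also a prespecification gap. With no stated model, the choice between an adjusted and an unadjusted comparison can be made after the data are seen, and so can the choice of sites behind the patient's PAL value. What is at stake is precision and freedom from post hoc choice.

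**Working it through.** **Inputs from the plan (Sample size):** difference 0.6 mm, SD 0.6 mm, power 0.9, alpha 0.05, 22 per arm.

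**Assumptions, not in the documents:** share of variance in change explained by the covariates (R²) from 0 to 25%; 30% smokers; block size 4 or 20; SD of 0.6 mm carried from the second reevaluation to day 168.

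**1. The plan's own figure.** For two means, n per arm = 2 x (z for alpha + z for power)² x (SD/difference)².
- Two-sided: 2 x (1.960 + 1.282)² x (0.6/0.6)² = 21.01, rounded up to 22. This matches.
- One-sided: 17.13, rounded up to 18. This does not match.

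With the t distribution, 22 per arm gives power 0.8997, and 23 would be needed for a full 90%.

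**2. Does 22 identify the analysis?** No. An ANCOVA at R² = 5%, calculated without an allowance for chance imbalance in baseline PAL, also needs 22 per arm (power 0.913).

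**3. Unadjusted comparison at 22 per arm.** Standard error = 0.6 x √(2/22) = 0.181 mm. With 42 df the t quantile is 2.018, so the 95% CI half-width is 2.018 x 0.181 = 0.365 mm. Power is 0.900.

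**4. ANCOVA at 22 per arm.** Two covariates leave 40 df (t quantile 2.021). The residual SD is 0.6 x √(1 − R²). Chance imbalance in baseline PAL, which is not stratified, inflates the variance by 1 + 1/40. At R² = 0 the half-width is 2.021 x 0.6 x √(2/22 x 1.025) = 0.370 mm.

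| Analysis | Power | Half-width (mm) |
|---|---|---|
| Unadjusted | 0.900 | 0.365 |
| ANCOVA, R² 0% | 0.892 | 0.370 |
| ANCOVA, R² 5% | 0.906 | 0.361 |
| ANCOVA, R² 10% | 0.921 | 0.351 |
| ANCOVA, R² 25% | 0.958 | 0.321 |

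The half-widths are equal when 1 − R² = 2.018² / (2.021² x 1.025), that is, at R² = 0.027. With blocks of 20 and R² = 0, simulated ANCOVA power is 0.887.

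**5. Smoking alone prognostic.** Simulation with 44 patients and permuted blocks within smoking stratum, allowing incomplete last blocks (150,000 runs for size, 60,000 for power at 0.6 mm):

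| Blocks | Smoking R² | Size, unadjusted | Power, unadjusted | Power, ANCOVA |
|---|---|---|---|---|
| 4 | 5% | 0.045 | 0.905 | 0.907 |
| 4 | 10% | 0.040 | 0.908 | 0.917 |
| 4 | 25% | 0.025 | 0.928 | 0.959 |
| 20 | 5% | 0.047 | 0.903 | 0.903 |
| 20 | 10% | 0.042 | 0.906 | 0.917 |
| 20 | 25% | 0.031 | 0.918 | 0.955 |

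The size of the ANCOVA stayed between 0.049 and 0.051. The unadjusted test is conservative, yet its power does not fall below the planned level.

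**6. Dependence on the SD.** The SD of 0.6 mm is not tied to day 168 or to a defined patient value. At SDs of 0.5, 0.7 and 0.8 mm, unadjusted power is 0.973, 0.793 and 0.681. ANCOVA at R² = 10% gives 0.981, 0.823 and 0.715. The SD matters far more than the covariates.

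**The case against.** The best reply is that an unadjusted comparison is a legitimate choice. It is unbiased, keeps about 0.90 power, and errs only towards caution. Whether adjustment helps depends on an R² that the documents do not give, and below about 3% it loses slightly. Simply naming an unadjusted test, with its patient-level value, would close the prespecification gap too. All of this stands: the ANCOVA is an improvement, not the repair of an invalid analysis. A site-level model with clustering by patient would be another defensible option.

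Three stronger readings are tempting, and the documents support none of them.
- A reader might infer that an unadjusted analysis would bias the result or leave the trial underpowered. The calculations show neither.
- A reader might infer from 2 x 22 that an unadjusted test is what the plan intends. The figure is compatible with one, but the plan states neither test nor sidedness, and an adjusted analysis can lead to the same number.
- A reader might infer that the sample size is safe whatever patient-level value is chosen. A full-mouth mean, deep sites only and the defect tooth could differ in both mean difference and SD. The plan does not say which of them its 0.6 mm figures describe.

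**Conclusion.** The point holds as a recommendation on precision and prespecification. No primary analysis is named, and the stratification factor and baseline PAL are not linked to one. Adjusting for both costs at most about one point of power (0.892 against 0.900, or 0.887 in simulation with large blocks) and 0.005 mm of half-width. At an assumed R² of 10% to 25% it brings power to 0.921 to 0.958 and the half-width to 0.351 to 0.321 mm. It also restores the nominal error rate if smoking is prognostic.

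These figures rest on the assumed ranges for R², smoking share and block size. They also require that the 0.6 mm difference and 0.6 mm SD hold at day 168 for the patient-level value eventually chosen. The plan ties its assumed control-group change to the second reevaluation and to no defined set of sites, so that condition is unproven.

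**What to change.** Before outcome data are seen, add to the Statistical analysis section:
- the primary analysis: an ANCOVA of patient-level PAL change from baseline to day 168 on treatment group, baseline PAL over the same sites, and smoking stratum, at two-sided alpha 0.05, reporting the adjusted mean difference with its 95% CI;
- the patient-level PAL summary that this model uses, that is, which sites are included and how they are aggregated.

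The model costs a few lines of text and two degrees of freedom. It needs no new data, and the covariates give no reason to change 2 x 22. Once the patient-level value is named, the sponsor should confirm that the 0.6 mm difference and 0.6 mm SD are meant for that value at day 168. If they are not, the sample size has to be recalculated, with or without covariates.

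### Does a sample size of 2×22 need an allowance for patients without a day-168 attachment level?

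*Combined protocol and SAP*

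**What the plan says.** All of this is in the combined protocol and SAP. Under Statistical analysis, Primary endpoint, the outcome is "the reduction of the probing attachment level (PAL) between baseline and the final study after 168 days". The Sample size paragraph starts from an "average reduction of an attachment level of -2.0 mm in the control group between baseline and second reevaluation" and a standard deviation of 0.6 mm. It then says that "the difference between the test and control group is 0.6 mm for a test strength of 0.9", sets the error probability at 0.05, and concludes that "a group size of 2×22 patients is required".

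The test and its sidedness are not named. No loss rate, replacement rule, separate recruitment figure or method for a missing close-out value appears anywhere in the document.

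Attachment level is also measured between baseline and close-out. At the first re-evaluation, "PAL, PPD, BoP, GI, and PCR will be re-recorded on all teeth". At the second, "The parameters PAL, PPD, BoP, GI and PCR will be reassessed in all study patients again". The Close out visit section places the final examination 84 days after the second re-evaluation.

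**The concern.** Two things catch the eye.

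First, 22 per arm is almost exactly what a two-sided calculation needs with complete data, so it seems to leave nothing for patients who do not return. The primary outcome is read at the last of four examinations, 84 days after the one before. If 44 is also the recruitment target and some patients miss close-out, the analysis will have less than the stated power of 0.9, and a real 0.6 mm advantage would be missed more often than the planned one time in ten.

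Second, the sample size sentence refers to the second re-evaluation and the primary endpoint to day 168. That raises the question whether the trial was sized for a different outcome from the one it will test.

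**Working it through.** **Inputs (Sample size paragraph).** Difference 0.6 mm, SD 0.6 mm, so standardised difference 0.6/0.6 = 1.0; error level 0.05; power 0.9; equal arms. *Assumed:* a two-sided comparison of two means.

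**Reproducing 22.**
- Normal approximation: n = 2 × (1.960 + 1.2816)² × (0.6/0.6)² = 21.01 per arm, rounded up to 22. Power at 22 is 0.9126.
- Noncentral t-test: n = 22.02 per arm. Power at 22 is 0.8997.
- One-sided at 0.05, t-test: n = 17.85, rounded up to 18. Power at 22 is 0.947.

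The two-sided reading reproduces the plan's figure, so it is the likely one. Under it, 22 is the complete-data number. Under the one-sided reading, 22 would hold a margin of four per arm.

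**Power with fewer complete patients (two-sided, same difference and SD).**

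| Complete per arm | t-test | Normal approximation |
|---|---|---|
| 22 | 0.900 | 0.913 |
| 21 | 0.885 | 0.900 |
| 20 | 0.869 | 0.885 |
| 19 | 0.851 | 0.869 |
| 18 | 0.830 | 0.851 |
| 17 | 0.807 | 0.830 |

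No single lost patient marks a threshold. The t-test is 0.0003 below 0.90 with nobody lost. The normal approximation is 0.906 with one patient lost (22 against 21) and 0.8998 with one lost in each arm.

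**Effect of an assumed loss rate.** The documents give none, so a range is shown. Mean power is the t-test power averaged over a binomial number of completers from 22 per arm. The enrolment that would leave 22 complete on average is 22/(1 − loss), rounded up.

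| Assumed loss | Mean power, 22 enrolled per arm | 22/(1 − loss) |
|---|---|---|
| 5% | 0.883 | 24 |
| 10% | 0.864 | 25 |
| 15% | 0.842 | 26 |
| 20% | 0.817 | 28 |

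The chance that all 44 complete is 0.98⁴⁴ = 0.41 at 2% loss, 0.95⁴⁴ = 0.10 at 5% and 0.90⁴⁴ = 0.01 at 10%.

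**Comparison with the other inputs.** With no loss at all, t-test power at 22 per arm is 0.85 if the SD is 0.65 mm and 0.79 if it is 0.7 mm. An SD only 0.05 mm larger than assumed costs about as much as three lost patients per arm (19 complete: 0.851).

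**What the analysis could recover.** Adjusting for a covariate with correlation r to the outcome reduces the variance by the factor 1 − r². To offset a fall from 22 to 20 per arm, r = √(1 − 20/22) = 0.30.

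**Visit label.** The intervals are 28 + 56 = 84 days to the second re-evaluation and 84 + 84 = 168 days to close-out, so the −2.0 mm refers to about day 84. The sample size formula contains only the difference, the SD, the error level and the power. The control mean appears nowhere in it. The 0.6 mm difference and 0.6 mm SD carry no visit label of their own.

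**The case for a change.** The best case for a change is that the direction is hardly in doubt. Attendance at four examinations over about six months is seldom perfect, and even at an assumed 2% loss the chance of 44 complete patients is only 0.41. At 10%, the risk of missing a true effect rises from about 0.10 to about 0.14. No analysis method is written down, so the plan cannot be credited with recovering that power by adjustment or by a repeated-measures model. Nothing suggests that the missing allowance was redacted.

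Much of this stands. The document is silent on loss and on missing close-out values, and on the two-sided reading 22 holds no meaningful reserve. What does not stand is the step from silence to a defect. The paragraph states a requirement; that exactly 44 will be recruited is an inference. The two-sided test behind the absence of a reserve is itself an inference, though a good one. The size of the loss is wholly assumed.

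On the visit label, it is fair to say that a reader cannot tell whether the difference and SD were meant for day 168. But nothing shows that other values apply there, and the one labelled quantity has no bearing on the sample size.

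**Conclusion.** No change follows. The 2×22 and the power of 0.9 agree with the plan's own inputs: 21.01 rounded up to 22 by the normal approximation, and 0.8997 by the t-test. No stated figure is therefore wrong. Whether the trial falls short of 0.9 depends on how many patients miss close-out, which the documents do not say.

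Over assumed losses of 5 to 20%, mean power would lie between about 0.88 and 0.82. That is a moderate cost, similar to a small misjudgement of the SD. Avoiding it would take 2 to 6 more patients per arm, which is an ordinary trade-off in a trial of this size. Recruiting a few patients above a required number is a routine decision and contradicts nothing in the document.

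The silence on a missing day-168 value is a gap that analysts can fill sensibly, because attachment level is already recorded at both re-evaluations and can be used in a repeated-measures model. The visit named beside the control mean is a clerical slip with no effect on the sample size.

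These conclusions assume a two-sided test and the plan's 0.6 mm difference and 0.6 mm SD at day 168. A one-sided test would leave slack at 22 and weaken the concern further.
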